4.1.2. Baseline Definition

For all endpoints the baseline value will be the latest pre-dose assessment with a non-missing value, including those from unscheduled visits and the screening visit. If time is not collected, Day 1 assessments are assumed to be taken prior to first dose and used as baseline. For endpoints assessed using an analysis set other than the Safety analysis set, the baseline value for subjects who are randomised and not dosed will be the latest assessment with nominal visit on or prior to Day 1.

Unless otherwise stated, if baseline data is missing no derivation will be performed and baseline will be set to missing.

4.1.3. Missing Data Handling Rules

- Missing data can occur due to study withdrawal or participants lost to follow-up before the completion of the study or due to intermittent missing values (i.e. data between two non-missing assessments).
- In addition, for the hypothetical estimands of the primary and secondary COVID-19 progression endpoints, data collected after the occurrence of an intercurrent event will be excluded from the analysis and will therefore be set to missing.
- For the primary and secondary COVID-19 progression endpoints, missing data will be imputed under a missing at random (MAR) assumption using a multiple imputation (MI) model. More details are provided in Section 6.2.8.

- For all other endpoints, a treatment policy strategy will be used for all intercurrent events where all data captured will be included in the summary and analysis, unless otherwise stated.

The following rules will be applied to viral load endpoints:

- The imputation logic when a sample is reported as 'NEG' (below lower-limit of detection) or '<2.08' (below lower-limit of quantification) is to impute as $0.5 \times 120 \text{ copies/ml} = 60 \text{ copies/ml} = 1.78 \log_{10} \text{ copies/ml}$
- Subjects who die prior to Day 8 (or Day 5 or Day 11), their AUC viral load value will be imputed using the worst AUC viral load value from other subjects in the same treatment arm who have completed Day 8 (5/11) and have a valid AUC(D1-8)/(D1-5)/(D1-11).
- If Day 8 assessment alone is missing but Day 5 and Day 11 assessments are available, the Day 8 will be imputed using linear interpolation between Day 5 and Day 11. AUC will be calculated then.
- If more than 2 consecutive assessments are missing prior to and including Day X, then the AUC(D1-X) will not be calculated.
- If a subject is lost to follow-up prior to Day X, then AUC(D1-X) will be set to missing.

4.2. Primary Endpoint Analyses

4.2.1. Definition of Primary Endpoint

The primary endpoint is the progression of COVID-19 through Day 29 as defined by hospitalization > 24 hours for acute management of illness due to any cause OR death.

The primary efficacy endpoint will primarily be assessed using an estimand that uses a hypothetical strategy to deal with the main intercurrent events as detailed in section 1.1.

4.2.2. Main analytical approach

The primary analysis will be conducted on the ITT analysis set, excluding participants who did not meet key inclusion/exclusion criteria (see section 4.2.2.1). All intercurrent events (see below) will be handled using a hypothetical strategy for the primary estimand, i.e. assuming the intercurrent event had not occurred.

The primary endpoint will be summarized using counts and percentages of the number of participants who have progression of COVID-19. The proportion of participants meeting the primary endpoint will be compared for sotrovimab 500 mg IM vs sotrovimab 500 mg IV using a 3.5% non-inferiority margin on the risk difference scale as per section 2.

The proportion of participants meeting the primary endpoint will be compared between treatments using a generalized linear model (GLM) from the binomial family with identity link, adjusted for treatment group (sotrovimab 500mg IV, sotrovimab 500mg IM), derived age group (<65 years old, ≥65 years old, see Section 6.2.7), and gender (female, male).

The absolute risk difference and associated 95% CI will be computed to test for non-inferiority in hypothesis (1).

Covariates may be removed from the model if it fails to converge as described in section 4.1.1. If the model still does not converge a GLM assuming a normal distribution for the endpoint and with identity link will be used, adjusted for the covariates above. If no events are observed on either treatment arm, the Farrington-Manning test will be used to compare arms.

The anticipated intercurrent events are:

- Not receiving randomized treatment or an alternative study treatment (i.e. treatment misallocation)
- Discontinuation of study intervention as described in Protocol Section 7.1.
- Use of medication not permitted during the study as listed in Protocol Section 6.8.1 up to day 29

Events are only deemed to be intercurrent events if they occur before occurrence of the primary endpoint. Data observed in the period following an intercurrent event (i.e. from the study day following the intercurrent event) will be excluded from the analysis. Data from this period will be assumed “missing at random” (MAR).

For participants that withdraw from the study and do not meet the primary endpoint at the time of withdrawal, data in the post-withdrawal period will also be assumed MAR.

Details of the method for multiple imputation is described in section 6.2.8.

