The COMET-TAIL study was then designed to assess the efficacy, safety, and tolerability of intramuscular (IM) sotrovimab versus intravenous (IV) sotrovimab when given to high-risk participants for the treatment of mild/moderate COVID-19. This study evaluated the clinical efficacy of two dose levels of IM sotrovimab compared with IV sotrovimab in preventing progression of COVID-19 by utilizing a non-inferiority (NI) design. Enrollment was completed on 19-AUG-2021 and the day 29 analysis indicated the following: in the IM administration (500mg) arm of the trial, there was a 2.7% rate of progression to hospitalization for more than 24 hours or death through Day 29 of the trial, compared to 1.3% in the IV administration arm (also 500 mg). The adjusted difference between the IM and IV arms of the trial was 1.11% with a 95% confidence interval (CI) of -1.24% to 3.45%. The upper bound of the 95% CI was within the predetermined 3.5% non-inferiority margin set for the trial’s primary endpoint in consultation with the US Food and Drug Administration (FDA).

VIR-7831  
Vir Biotechnology, Inc.

VIR-7831-5008 (GSK Study 217114)  
Amendment 4

Since then, several factors have contributed to the need for evaluation of different doses of sotrovimab. First, the development of the Omicron variant and its sublineages has caused the landscape to evolve substantially as described in the COVID-19 treatment guidelines from the NIH ([COVID-19 Treatment Guidelines Panel 2022](#)). Understanding the safety and tolerability of sotrovimab across a broader dose range will provide the data should a higher dose of sotrovimab be required to treat a variant that is less susceptible to sotrovimab in the future. Additionally, evaluation of sotrovimab across a range of doses will allow for additional clinical pharmacology evaluation of population PK parameters.

Thus, this study will now consist of two parts, the original protocol and the safety substudy. In the safety substudy, the aim will be to evaluate the safety and tolerability of a single ascending dose of sotrovimab when given for the treatment of mild/moderate COVID-19 to participants at high risk of disease progression. It will also evaluate the safety and tolerability of different infusion times. The existing non-clinical and clinical safety data support the evaluation of sotrovimab across the range of doses in this substudy.

Approved

VIR-7831  
Vir Biotechnology, Inc.

VIR-7831-5008 (GSK Study 217114)  
Amendment 4

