- Population: All participants in the Intent-to-Treat (ITT) analysis set excluding participants who did not meet key inclusion/exclusion criteria (see section 4.2.2.1).
- Endpoint: Progression of COVID-19 through Day 29 as defined by hospitalization > 24 hours for acute management of illness due to any cause or death
- Summary measure: Absolute difference in the proportion of participants meeting the primary endpoint
- The anticipated intercurrent events are:
 - Not receiving randomized treatment or an alternative study treatment (i.e. treatment misallocation)
 - Discontinuation of study intervention as described in Protocol Section 7.1.
 - Use of medication not permitted during the study as listed in Protocol Section 6.8.1 up to Day 29

All intercurrent events will be handled using a hypothetical strategy where data collected after the occurrence of an intercurrent event will be excluded from the analysis, i.e. assuming the intercurrent event had not occurred.

Rationale for estimand: A hypothetical estimand is used as this is considered more conservative than treatment policy and therefore more appropriate for a non-inferiority comparison.

Supplementary Estimand for the Primary Endpoint

A supplementary estimand will be conducted based on all participants in the ITT analysis set by handling all intercurrent events with a treatment policy strategy (i.e. regardless of the intercurrent events occurring), with all the other attributes being the same as in the primary estimand. To estimate this estimand, all data collected in the ITT analysis set up to Day 29 will be included in the analysis.

[figure not shown]
[figure not shown]
Estimands for Key Secondary Endpoints

The estimand for the secondary endpoint 'Mean area under the curve of SARS-CoV-2 viral load in nasal secretions as measured by qRT-PCR from Day 1 to Day 8 (AUC_{D1-8})' is described by the following attributes:

- Population: All participants in the Virology analysis set, as defined in Section 3
- Summary measure: Treatment ratio (IM/IV) of mean \log_{10} AUC_{D1-8}
- Intercurrent events: Death and use of medication not permitted during the study as listed in Protocol Section 6.8.1 up to day 8
 - Strategy for Death: Composite strategy, where for participants who die prior to Day 8, the AUC_{D1-8} viral load value will be imputed using the worst AUC_{D1-8} viral load value from other participants in the same treatment arm.

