2. STATISTICAL HYPOTHESES

The primary objective of this study is to evaluate the efficacy of IM sotrovimab versus IV sotrovimab in preventing the progression of mild/moderate COVID-19 in a non-inferiority comparison.

The primary endpoint is progression of COVID-19 through Day 29 as defined by hospitalization > 24 hours for acute management of illness OR death.

Denoting the proportions of participants with progression of COVID-19 by Day 29 in the sotrovimab 500 mg IM arm, sotrovimab 250 mg IM arm and sotrovimab 500 mg IV arm as P_{IM500} , P_{IM250} and P_{IV500} , respectively, then the null (H_0) and alternative (H_A) hypotheses are as follows using a non-inferiority margin of 3.5% (per feedback from the FDA, as mentioned in protocol section 4.2) on the risk difference scale:

(1) Sotrovimab 500 mg IM vs sotrovimab 500 mg IV:

- $H_0: P_{IM500} - P_{IV500} \geq 3.5\%$. $H_A: P_{IM500} - P_{IV500} < 3.5\%$

(2) Sotrovimab 250 mg IM vs sotrovimab 500 mg IV:

- $H_0: P_{IM250} - P_{IV500} \geq 3.5\%$. $H_A: P_{IM250} - P_{IV500} < 3.5\%$

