4.3.2. Main Analytical Approach

4.3.2.1. Binary Endpoints

The following secondary endpoints will be summarised/analysed as binary endpoints:

- Participants who have progression of COVID-19 (emergency room, hospitalisation for any duration or cause, death) through Day 29
- Proportion of Participants Who Progress to Develop Severe or Critical Respiratory COVID-19 at Day 8, 15, 22 and 29
- Proportion of participants with a persistently high SARS-CoV-2 viral load at Day 8 by qRT-PCR

The secondary binary endpoints will be summarized using counts and percentages.

Participants who have progression of COVID-19 (emergency room, hospitalisation for any duration or cause, death) through Day 29 will be analysed as per the primary endpoint (hypothetical and treatment policy estimands).

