5. SAMPLE SIZE DETERMINATION

Sotrovimab IM participants and sotrovimab IV participants were planned to be enrolled and randomized in a 1:1:1 ratio to receive a single dose IV infusion of sotrovimab or a single IM injection of sotrovimab at one of two dose levels, in an open-label manner.

Approximately 1020 (340 per arm) participants were planned to be randomly assigned to study intervention. This sample size will provide approximately 90% power to demonstrate that IM

injection of sotrovimab is non-inferior to IV infusion of sotrovimab in terms of the proportion of participants with progression of COVID-19 through Day 29 at the one-sided 2.5% significance level assuming COVID-19 progression rates of 2% in the sotrovimab IM and IV arms and 3.5% non-inferiority margin on the risk difference scale.

Following the discontinuation of sotrovimab 250 mg IM arm (See Section 4.7), no more participants were enrolled and randomized into this arm. The remaining participants were randomized in a 1:1 ratio to receive sotrovimab 500mg IV or sotrovimab 500 mg IM

Sample Size/Power Sensitivity

The table below shows power for showing non-inferiority for different true progression rates on the sotrovimab IV arm and when the progression rate in the sotrovimab 500mg IM arm is equal to or higher than that on IV, given a sample size of N=340 per arm.

		Progression rate in sotrovimab IV arm		
		1.0%	1.5%	2.0%
Progression rate in sotrovimab IM arm minus Progression rate in sotrovimab IV arm	0% (equal)	>99%	96%	90%
	+0.1%	99%	95%	88%
	+0.2%	98%	93%	85%
	+0.3%	97%	91%	82%

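### The primary model estimates the stated difference in proportions only if the risk difference is the same in every age-by-gender stratum; if the IM excess is larger in higher-risk participants, false non-inferiority becomes more likely

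*SAP*

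**What the plan says.** SAP section 2 writes the hypotheses in arm-level quantities ("Denoting the proportions of participants with progression of COVID-19 by Day 29 in the sotrovimab 500 mg IM arm", and likewise for IV). The null is that P_IM500 minus P_IV500 is at least 3.5%. The primary estimand in SAP 1.1 agrees: "Summary measure: Absolute difference in the proportion of participants meeting the primary endpoint". Neither place mentions weighting by stratum.

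SAP 4.2.2 has the proportions "compared between treatments using a generalized linear model (GLM) from the binomial family with identity link", adjusted for treatment, age group (<65, ≥65) and gender. No treatment-by-covariate term, standardisation step or robust variance is given. After non-convergence a covariate may be removed under SAP 4.1.1, which considers removal when one category dominates that covariate. The last step is: "If the model still does not converge a GLM assuming a normal distribution for the endpoint and with identity link will be used".

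The same model feeds the tipping-point analysis (SAP 4.2.4). It also feeds the secondary endpoint of emergency room visit, hospitalization or death, which "through Day 29 will be analysed as per the primary endpoint (hypothetical and treatment policy estimands").

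**The concern.** A main-effects identity-link model imposes one common risk difference on all strata. Binomial maximum likelihood weights strata roughly by n/[p(1-p)], so low-risk strata dominate. If the true risk difference varies with baseline risk, the coefficient is a weighted average that departs from the difference in arm proportions.

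If IM multiplies risk by about the same factor in both age groups, the absolute excess falls mainly on older participants. They carry the least weight, so the estimate is too small and an IM arm at the margin passes too often. The quantity tested also depends on convergence. Under 1:1 allocation the normal identity-link fallback targets the overall difference, whereas the binomial model does not unless the risk difference is constant.

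The primary non-inferiority claim is at stake, together with its sensitivity analysis and the secondary non-inferiority test.

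**Working it through.** **The plan's own figure.** SAP section 5 says "This sample size will provide approximately 90% power" "at the one-sided 2.5% significance level", with 2% in both arms, a 3.5% margin and 340 per arm. SE = √(2×0.02×0.98/340) = 0.01074, and power = Φ(0.035/0.01074 − 1.96) = 90.3%. This reproduces the stated figure. It is a calculation for the crude difference in proportions.

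**Assumptions not in the documents.** 20% aged ≥65 (the Protocol gives this target in section 5.1.1 for the substudy only); age risk ratio 2 to 4; constant IM/IV risk ratio; no gender effect; complete data. The IV rate is 1.3% (the reported rate) or 2.0% (the planning rate).

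**Worked example: IV 1.3%, age risk ratio 3, true difference 3.5 points.**
- IV risks: <65, 1.3/(0.8 + 0.2×3) = 0.929%; ≥65, 2.786%.
- IM/IV risk ratio: 4.8/1.3 = 3.692. IM risks: 3.429% and 10.286%.
- Stratum differences: 2.50 and 7.50 points. Overall: 0.8×2.50 + 0.2×7.50 = 3.50.
- Variance of each stratum difference, up to a common factor: <65, [0.00929×0.99071 + 0.03429×0.96571]/0.8 = 0.0529; ≥65, [0.02786×0.97214 + 0.10286×0.89714]/0.2 = 0.5968.
- Inverse-variance weights: 18.91 and 1.68, so 91.9% goes to those under 65 against their 80% share.
- Weighted difference: 0.919×2.50 + 0.081×7.50 = 2.91 points.

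The exact large-sample limit of the maximum-likelihood coefficient (treatment and age in the model) is 2.95. For age risk ratios 2 and 4 it is 3.29 and 2.65. At IV 2.0% and ratio 3 it is 2.94.

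**Simulated rejection at a true difference of exactly 3.5 points.** 340 per arm, SAP fallbacks applied, 2,500 to 8,000 trials per scenario. Ranges span separate runs and different rules for which covariate is dropped.

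| Age risk ratio | IV 1.3% | IV 2.0% |
|---|---|---|
| 2 | 7.4-7.6% | 5.6-7.0% |
| 3 | 9.5-12.8% | 8.0-10.1% |
| 4 | 12.9-18.6% | 11.5-17.2% |

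The choice of dropped covariate matters. In one run at IV 1.3%, dropping gender gave 12.3% and 18.6% for ratios 3 and 4; dropping age gave 9.5% and 12.9%. With 3,000 trials the simulation SE at 18.6% is √(0.186×0.814/3000) = 0.7 points.

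**Comparators and other patterns.**
- Crude Wald or least squares, constant risk ratio: about 3-4%.
- SAP procedure with a constant risk difference: about 3.5-4.7%.
- SAP procedure with the excess larger in low-risk participants: 2.9-3.0%.
- 2,000 per arm, IV 2.0%, ratio 3, constant risk ratio: 18.6-19.9%, against 2.6-2.9% for crude Wald. The effect is therefore systematic and grows with sample size.
- Full-model convergence at 340 per arm, IV 2.0%: 74%, 72% and 66% of trials for ratios 2, 3 and 4. Among those fits, rejection was 6.7%, 10.4% and 16.2%, so the fallbacks dilute the error.

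**The case against.** The identity-link binomial model is a recognised, prespecified way to obtain an adjusted risk difference, and it is correct if the risk difference is homogeneous. The documents give no progression rates by age and no pattern for the IM effect, so the inflation rests on two assumed features. SAP 4.2.2 reports counts and percentages by arm, and SAP 4.6.1 summarises progression by age and sex, so marked heterogeneity would be visible. All of this stands. None of it corrects the test, because those summaries are descriptive and do not enter the decision rule.

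Three stronger readings are tempting and not supported.
- *The error is 7-18% instead of 2.5%.* That holds only with a clear age gradient and an excess concentrated in high-risk participants. At this sample size a fair comparator is about 3.5%, since a crude Wald bound already exceeds 2.5%.
- *The bias always favours IM.* It does not: the direction depends on the pattern, and with the reverse pattern the coefficient limit is 3.68, above the true 3.50.
- *The reported result shows the effect.* The Protocol synopsis gives an adjusted difference of 1.11% (95% CI −1.24% to 3.45%), against a crude 2.7 − 1.3 = 1.4 points. Covariate imbalance or imputation could explain the gap, and the analysed N and the model finally fitted are not given. Adding the adjusted half-width, (3.45 + 1.24)/2 = 2.345, to 1.4 gives 3.745, but that mixes two estimators. A crude Wald bound with an assumed 340 per arm is 1.4 + 2.10 = 3.50. The mechanism should also narrow the interval: simulated converged fits at 1.3% and 2.7% with ratio 3 had an average half-width of 1.96, against 2.19 for crude Wald. The reported 2.345 is wider than both.

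**Conclusion.** The mismatch between the stated quantity and the tested one is in the SAP text. Its consequence is conditional. Under a constant IM/IV risk ratio, with 20% aged ≥65, 340 per arm and IV rates of 1.3-2.0%, false non-inferiority at the margin is about 6-8%, 8-12% and 12-18% for age risk ratios 2, 3 and 4. The position within each range depends partly on which covariate is dropped. If the risk difference is constant, or larger in low-risk participants, there is little or no inflation beyond the usual small-sample excess. The documents do not show which case applies. A primary test should not depend on an unstated homogeneity assumption when an estimator of the stated quantity is available. The reported Day 29 figures neither confirm nor refute the effect.

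**What to change.** In SAP 4.2.2, 4.2.4 and 4.3.2.1, make the tested quantity the standardised (marginal) risk difference:
- Fit a logistic model with treatment, age group and gender.
- Average the predicted risks over all participants under IM and under IV, and take the difference.
- Use a delta-method or influence-function SE, combine over imputations by Rubin's rules, and compare the upper bound with 3.5%.

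Alternatively, make the SAP's existing normal identity-link GLM, with robust SE, the main analysis. In either case keep the binomial identity-link result as supportive and show the crude difference beside it.

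The Day 29 result is already reported, so replacing its primary estimator now would be a post-hoc change. For that result, present the standardised difference and its bound beside the prespecified one.

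Cost: SAP wording and a little programming, with no new data. Simulated power at equal rates with age risk ratio 3 goes from 93.7% to 90.1% at the 2% planning rate, still the stated 90%, and from 97.9% to 97.3% at 1.3%. The upper bound may be less favourable.

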2.1. Multiplicity Adjustment

Hypotheses (1) and (2) above will be tested using the primary estimand according to the hierarchical testing principal as follows:

- If the null hypothesis for (1) is rejected, i.e., the upper bound of the two-sided 95% confidence interval for the risk difference between sotrovimab 500 mg IM and

sotrovimab 500 mg IV is less than the pre-specified 3.5% non-inferiority margin, then hypothesis for (2) will be tested.

- If the null hypothesis for (1) is not rejected, then hypothesis for (2) will not be tested.

Below is a summary of possible outcomes of the hierarchical testing procedure:

Which Null Hypothesis is Rejected	Non-inferiority Declared For
Hypotheses (1) and (2)	Both sotrovimab 500 mg IM and sotrovimab 250 mg IM (vs. sotrovimab 500 mg IV)
Hypothesis (1) but Not (2)	Only sotrovimab 500 mg IM vs. sotrovimab 500 mg IV
Hypothesis (1) is NOT rejected (Null hypothesis for (2) won't be tested in this case)	Neither sotrovimab 500mg IM nor sotrovimab 250mg IM (vs sotrovimab 500mg IV)

Two secondary endpoints will be formally analysed:

- 1) Mean area under the curve of SARS-CoV-2 viral load in nasal secretions as measured by qRT-PCR from Day 1 to Day 8 (AUC_{D1-8}). Each IM dose will be assessed for equivalence to IV based on the two-sided 90% confidence interval for the treatment ratio falling within equivalence bounds of 0.5 to 2.0.
- 2) Progression of COVID-19 through Day 29 as defined by visit to a hospital emergency room for management of illness OR Hospitalization for acute management of illness for any duration and for any cause OR Death. Each IM dose will be assessed for non-inferiority vs IV using a non-inferiority margin of 3.5% on the risk difference scale.

The testing of the two secondary endpoints above is adjusted for multiplicity by using the following hierarchy:

- Secondary endpoint (1) will only be tested if non-inferiority is achieved for sotrovimab 500 mg IM vs. sotrovimab 500 mg IV and sotrovimab 250 mg IM vs. sotrovimab 500 mg IV comparisons for the primary endpoint.

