4. STATISTICAL ANALYSES

4.1. General Considerations

4.1.1. General Methodology

The ITT Analysis Set will be used for all Study Population analyses and Efficacy analyses, unless otherwise specified. A subset of the ITT analysis set will be used for the primary estimand, excluding participants who did not meet key inclusion/exclusion criteria (see 4.2.2). The Safety Analysis Set will be used for selected Study Population summaries and all safety analyses. The PK analysis Set will be used for all PK analyses. Virology analysis set will be used for all Virology analyses.

In the case of a difference between the stratification assigned at the time of randomization and the data collected in the eCRF, the analyses will be performed based on the data collected in the eCRF, not the assigned stratum at randomization. All analyses will be adjusted for treatment group (sotrovimab 500mg IV, sotrovimab 500mg IM), derived age group (<65 years old, ≥65 years old, see Section 6.2.7), and gender (female, male). Stratification factors of region and vaccination status are not included as covariates due to the small number of non-US and partially/fully vaccinated participants in the ITT analysis set. In addition the 12-17 years old and 18-64 years old categories are combined due to the small number of participants in the 12-17 years old category.

In the case of model convergence issues, if one category dominates within a particular covariate then that covariate may be considered for removal from the model.

Confidence intervals will use two-sided 95% confidence levels unless otherwise specified.

Unless otherwise specified, continuous data will be summarized using descriptive statistics: n, mean, standard deviation (std), median, minimum and maximum. For log-transformed data (e.g. AUC) descriptive statistics will present the geometric mean, standard deviation (SD of log-transformed data) and coefficient of variation. Categorical data will be summarized as the number and percentage of participants in each category.

Efficacy data will be reported according to nominal time of clinical visits unless otherwise stated. Hospitalization status, oxygen supplementation and healthcare resource utilization use will be slotted against the clinical visit date for summaries and analyses by visit.

All data will be reported according to the nominal time of clinic visits and assessments as specified in the protocol unless stated otherwise:

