4.2.4. Sensitivity analyses

To assess the sensitivity of the results to the missing data, a tipping point analyses will be performed for the hypothetical and treatment policy estimands. The underlying response rate among those subjects with missing response status in each arm will be varied ranging between 0 and 1. This analysis will be two-dimensional, i.e. it will allow for assumptions about the assumed response rate (and thus missing outcomes) in the two treatment arms to vary independently. For combinations of the assumed response rates in the arms, the number of additional responders among subjects with missing response will be imputed multiple times by drawing from a binomial distribution. The absolute difference and associated standard error for each imputed dataset will be calculated using the primary analysis model and results combined using Rubin's rules to calculate the risk difference and the 95% CI for the treatment comparison. Results will be presented via a heatmap.

In addition, a summary of the number of COVID-19 progressions through Day 29 (as defined in section 4.2.1) for the hypothetical estimand will be provided for the split by those progressions that occur <3 days and ≥ 3 days post-dose.

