6.2.8. Statistical Modelling - Multiple Imputation

Multiple imputation will be used to impute data that is missing following withdrawal of the subject from the study, or following an intercurrent event for hypothetical estimands (if applicable), for the following two binary endpoints:

- Progression of COVID-19 through Day 29 as defined by hospitalization > 24 hours for acute management of illness due to any cause or death

- Progression of COVID-19 through Day 29 as defined by visit to a hospital emergency room for management of illness or hospitalization for acute management of illness for any duration and for any cause or death

Multiple imputation of endpoint data will be performed to impute data post study withdrawal or intercurrent event, as follows:

- Data will have a monotone missing structure so there will be no intermittent missing data.
- Imputation of missing data will proceed iteratively for each study day starting with Day 2 and ending at Day 29 using a logistic regression imputation model including the analysis model covariates and a parameter for COVID-19 progression status for the previous study day, i.e. imputation of COVID-19 progression status at Day X will include a covariate for status at Day X-1 from the previous imputation step.
- The “likelihood=augment” option in PROC MI will be used in the imputation to avoid quasi complete separation of data for the preceding timepoint covariate included in the imputation model. If logistic regression step fails to converge the following back-up options may be used:
 - i) A discriminant function [Brand, 1999] may be used in place of logistic.
 - ii) MCMC with adaptive rounding.

A sufficient number of imputations will be performed to ensure the stability of the estimates. The results of analysis from each complete imputed dataset will be combined using Rubin’s rule.

Table 3 Multiple Imputation Specifications) details the models, covariates and the seed to be used for the analyses.

Table 3 Multiple Imputation Specifications

Endpoint	Model	Covariates	Post-Baseline Timepoints Included in Prediction Model for Day X (X=2,...,29)	Initial Seed
Proportion of participants who have progression of COVID-19 at Day 29 (hospitalized >24h/death)	Monotone Binary Logistic Regression	Treatment, Age Group at Baseline, Sex	Day X-1	6862

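### SAP Section 5 pairs about 90% power with a one-sided 2.5% level, but the Wald rule behind that power has an exact unadjusted error of 3.4–3.8%

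*SAP*

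**What the plan says.** SAP 2.1 decides the comparison of 500 mg IM with 500 mg IV by whether "the upper bound of the two-sided 95% confidence interval for the risk difference" lies below the 3.5% margin. SAP 4.2.2 compares the arms "using a generalized linear model (GLM) from the binomial family with identity link, adjusted for treatment group", age group and gender, and then states: "The absolute risk difference and associated 95% CI will be computed to test for non-inferiority in hypothesis (1"). SAP 4.1.1 fixes the confidence level but not the method: "Confidence intervals will use two-sided 95% confidence levels unless otherwise specified". The Farrington-Manning test appears in 4.2.2 only as a fallback when no events are observed.

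Two other places indicate how the interval is built. For the tipping-point analysis, SAP 4.2.4 says "The absolute difference and associated standard error for each imputed dataset will be calculated using the primary analysis model", with pooling by Rubin's rules to give the 95% CI. For the multiple imputation, SAP 6.2.8 says "The results of analysis from each complete imputed dataset will be combined using" Rubin's rule.

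SAP Section 5 states that 340 per arm give approximately 90% power "at the one-sided 2.5% significance level assuming COVID-19 progression rates of 2% in the sotrovimab IM and IV arms and 3.5% non-inferiority margin". Its sensitivity table gives power for IV rates of 1.0, 1.5 and 2.0% and true differences of 0 to 0.3 points.

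The current protocol (Amendment 4) covers a descriptive safety substudy. Its synopsis rationale still reports the Day 29 result of this comparison, an adjusted difference of "1.11% with a 95% confidence interval (CI) of -1.24% to 3.45"%.

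**The concern.** With progression rates near 2%, a Wald limit for a risk difference is not well calibrated. When the true difference equals the margin, trials that happen to see few IM events get both a small difference and a small standard error. The upper limit therefore falls below 3.5% too often.

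If the power in Section 5 was computed for that rule, the stated pair of 90% power and 2.5% one-sided error does not belong to one test. A reader would credit the design with tighter error control than the calculation gives, or with more power than a test that holds 2.5% would have. Secondary endpoint (2) has the same margin and, under SAP 4.3.2.1, the same analysis, so the question carries over to it.

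**Working it through.** **Inputs.** From SAP 2, 2.1 and 5: margin M = 3.5 points, 340 per arm, one-sided 2.5% (z = 1.96), IV rates p of 1.0, 1.5 and 2.0%, true differences δ of 0 to 0.3 points. Section 5 states no allowance for dropout and none is used here. The rate of 1.3% is the IV rate reported in the protocol rationale.

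**Step 1: reproduce the plan's figures.** The unpooled (Wald) formula is power = Φ((M − δ)/SE − 1.96), with SE = √{[p(1−p) + (p+δ)(1−p−δ)]/340}.

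At p = 2% and δ = 0: SE = √(2 × 0.02 × 0.98/340) = 1.074 points; 3.5/1.074 − 1.96 = 1.30; Φ(1.30) = 90.3%. The matching sample size is (1.96 + 1.282)² × 2 × 0.02 × 0.98/0.035² = 336.2, so 337 per arm against 340 planned.

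Computed power, with the SAP's figure in brackets:

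| δ (points) | IV 1.0% | IV 1.5% | IV 2.0% |
|---|---|---|---|
| 0 | 99.6 (>99) | 96.4 (96) | 90.3 (90) |
| 0.1 | 99.2 (99) | 94.8 (95) | 87.9 (88) |
| 0.2 | 98.5 (98) | 92.9 (93) | 85.1 (85) |
| 0.3 | 97.5 (97) | 90.6 (91) | 82.0 (82) |

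All 12 cells agree as rounded; the two that look a point off are 98.48 and 97.46 before rounding. The Farrington-Manning formula does not fit: its first row is 95.0, 88.2 and 81.2%.

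**Step 2: exact error of that rule.** Enumerate all 341 × 341 outcomes of two independent binomials with 340 per arm. Set the true IM rate to p + 3.5 points and add the probabilities of the outcomes that lead to a claim. The Wald rule claims when difference + 1.96 × unpooled SE < 3.5 points. The Farrington-Manning rule claims when (difference − 3.5 points)/SE₀ < −1.96, with SE₀ from rates estimated under a difference of exactly 3.5 points.

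| IV rate | Wald error | Farrington-Manning error |
|---|---|---|
| 1.0% | 3.82% | 1.95% |
| 1.3% | 3.69% | 2.03% |
| 1.5% | 3.62% | 2.08% |
| 2.0% | 3.44% | 2.21% |

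Monte Carlo with 2 million draws per rate gave 3.82, 3.64 and 3.45% for the Wald rule at 1.0, 1.5 and 2.0%. The excess is not peculiar to 340: at eight arm sizes from 320 to 385 the Wald error at these three rates was 3.1–4.2%.

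**Step 3: exact power at 2% in both arms.** Wald 89.5%; Farrington-Manning 82.8%.

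**Step 4: what the reported interval shows.** Its midpoint is (−1.24 + 3.45)/2 = 1.105, against an estimate of 1.11, so it is symmetric to rounding, as a Wald interval would be. Its half-width is (3.45 + 1.24)/2 = 2.345 points. A crude complete-data Wald half-width at 2.7% and 1.3% with 340 per arm is 1.96 × √[(0.027 × 0.973 + 0.013 × 0.987)/340] = 2.10 points. Imputation, covariate adjustment or smaller analysed arms could each explain the wider interval. The documents do not say which.

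**The case against.** The strongest reply is that SAP 4.2.4 and 6.2.8 already make an estimate-plus-SE interval the natural reading, so leaving it unnamed in 4.2.2 is missing detail that one sentence would cure. That stands. A reader might infer that the SAP leaves the deciding interval open; the two sections do not support that.

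A second reply is that 3.4–3.8% is not the level of the planned test, which is covariate-adjusted and multiply imputed. That also stands. A simulation of the day-by-day imputation with the adjusted Wald model (5,000 trials, with an assumed augmentation weight and with imputed progression kept once it occurred) gave 3.4–4.2% with 1% missing, 2.3–2.6% with 3% and 0.9–1.7% with 6%. These values rest on assumed settings and are only indicative, but they show that the direction is not fixed.

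Third, approximately 90% is accurate for the Wald rule, whose exact power is 89.5%. True, but Section 5 attaches that power to a 2.5% level, and the same rule does not have that level in the setting in which the power was computed.

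Fourth, the Day 29 results are already reported and the current protocol tests no hypothesis. This limits the remedy to disclosure and a sensitivity analysis. It does not make the stated pair correct.

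**Conclusion.** The pairing in SAP Section 5 is wrong as written. The calculation behind the 90% belongs to a Wald rule with an exact one-sided error of 3.4–3.8% over the SAP's own range of IV rates. A Farrington-Manning test keeps the error at 2.0–2.2%, with power of about 83% at 2% in both arms, roughly 7 points lower (89.5 − 82.8 = 6.7).

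These figures assume two independent binomials, 340 per arm, no covariates and no missing data. No document gives the level of the full adjusted and imputed procedure; it may be above, near or below 2.5%.

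A reader might go further and infer that the reported non-inferiority finding is an artefact of the interval, because 3.45% is only 0.05 points inside the margin. The documents do not support this. They give neither the analysed arm sizes nor the amount of imputed data, so whether another bound would cross 3.5% cannot be worked out from them.

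**What to change.** - **SAP Section 5:** state that the 90% power refers to a Wald rule whose exact unadjusted error is 3.4–3.8% at IV rates of 1.0–2.0%, and that power at 2% in both arms is about 83% with a Farrington-Manning test, which keeps the error below 2.5%.
- **SAP 4.2.2:** state that the deciding interval is the Wald-type interval from the primary model, pooled by Rubin's rule. Add a Farrington-Manning (score-type) bound at the 3.5% margin as a sensitivity analysis, and say how it is applied to the imputed data. Do the same for secondary endpoint (2). Label both post hoc, because Day 29 results are already reported.
- **Full procedure:** report a simulated type I error for the complete sequence of adjustment, fallbacks, imputation and pooling, at the amount of missing data actually seen.

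The cost is a less favourable stated power, one extra analysis that drops the planned covariates and is somewhat conservative, and one simulation. No more patients are needed, and the primary analysis stays as planned.
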